Official title: Efficacy of two sonic toothbrushes in reducing extrinsic tooth stain: An 8-week randomized clinical trial

NCT number: NCT05202093

Document date: 01/18/2022

Study Protocol and Statistical Analysis Plan

Study Design

This randomized, investigator-blinded, parallel-group clinical trial compared three toothbrush interventions. The study protocol was approved by the Institutional Review Board of Guanghua School of Stomatology, Sun Yat-sen University (Guangzhou, China). The eight-week study was conducted in full accordance with the ethical principles outlined in the World Medical Association Declaration of Helsinki. The trial was registered at ClinicalTrials.gov under the identifier NCT05202093, first submitted on Jan 07, 2022. It was conducted at the Guanghua School of Stomatology, Sun Yat-sen University, from March to July 2022.

Sample size calculation

Based on data from a previous clinical study evaluating the tooth stain removal efficacy of a whitening product, the sample size for the present trial was calculated. Assuming a standard deviation of 0.5 for Lobene stain area scores, a sample size of 40 participants per group was determined to be necessary at baseline. This calculation was designed to detect a 20% difference between groups with 80% statistical power at a significance level of $\alpha = 0.05$, while also accounting for a 10% attrition rate.

Study population

Adults residing in Guangzhou were invited to participate in the study. Prior to enrollment, the study details were thoroughly explained to all potential participants to ensure a full understanding of the purpose and procedures. Written informed consent was obtained from each individual. Participants were subsequently enrolled based on the inclusion and exclusion criteria. The inclusion criteria were: 1) aged 18-70 years; 2) good general health; 3) ability to attend all scheduled visits over the 8-week study period; 4) possession of more than 20 natural permanent teeth, excluding third molars, which are free of crowns or extensive restorative materials; 5) at least 12 anterior teeth suitable for scoring (i.e., free of crowns, veneers, large restorations, trauma, or non-vital pulp); 6) a whole-mouth mean Lobene stain composite score greater than 1. Exclusion criteria included: 1) severe oral or systemic diseases; 2) advanced periodontal diseases; 3) pregnancy or lactation; 4) dental fluorosis or tetracycline

staining; 5) orthodontic appliances or partial removable dentures; 6) participation in other clinical trials; 7) professional prophylaxis within 3 months or tooth whitening within 6 months; and 8) known allergy to study products.

Randomization

Eligible patients were assigned computer-generated random numbers in ascending order as they were enrolled in the study by an external dentist. They were then randomly allocated to one of three groups. The external dentist responsible for randomization maintained exclusive access to the group allocation information throughout the trial. All other study personnel remained blinded to the randomization information during the study.

Intervention

Patients in test group 1 were given the Oclean Digital Visual toothbrush (2.16 N·cm torque), patients in test group 2 received the Oclean Sonic Electric toothbrush (1.96 N·cm torque), and patients in the control group were provided with the Oral-B Classic 40 soft regular manual toothbrush.

Patients received their assigned toothbrushes along with the same toothpaste. The distribution of the study products occurred at a separate location. One study member was responsible for distributing the study products, while all other study members remained unaware of group assignments throughout the study.

Patients were instructed to brush their teeth twice daily (once in the morning and once in the evening) for one minute each session, using only the provided products, while maintaining their usual diet and oral hygiene habits.

Clinical assessments

Clinical examinations were conducted at baseline, 4 weeks, and 8 weeks by a single investigator who was unaware of the type of toothbrush used by each patient. The examinations included assessments of tooth stain as well as evaluations of both soft and hard oral tissues. Tooth stain was assessed on the buccal surfaces of six maxillary anterior teeth and on both the buccal and lingual surfaces of six mandibular anterior teeth using the Lobene Stain Index[30]. Each tooth surface was divided into two regions: the gingival region and the body region. The Lobene Stain Index quantifies

both the area and intensity of extrinsic tooth stain. The stain intensity was scored on a scale from 0 to 3, with the following criteria: 0 = no stain; 1 = light stain (yellow to light brown or gray); 2 = moderate stain (medium brown); and 3 = heavy stain (dark brown to black). Stain area was also scored on a scale from 0 to 3, based on the proportion of the tooth surface covered by stain, using these criteria: 0 = no stain detected; 1 = stain covering up to one-third of the region; 2 = stain covering more than one-third to two-thirds of the region; and 3 = stain covering more than two-thirds of the region. The composite score was calculated as the product of the stain area and intensity scores. The mean Lobene stain area, intensity, and composite scores were determined by summing the scores from all assessed regions of the tooth surfaces and dividing by the total number of regions evaluated.

A comprehensive examination of the oral soft and hard tissues was conducted to identify any abnormalities. The assessment included the soft and hard palate, oral mucosa, tongue, sublingual and submandibular regions, salivary glands, and the pharyngeal and laryngeal areas.

At each follow-up, an investigator asked patients about any adverse events during product use, including brushing discomfort, allergic reactions, and changes in oral soft tissues. General health changes related to the product were also monitored throughout the study.

After each examination session, the collected data were securely stored by a designated study facilitator. Other study personnel had no access to participant data during the study.

Statistical analysis

Statistical analyses were performed to assess differences among the three groups. Chi-square test and one-way analysis of variance (ANOVA) were utilized to compare the differences among treatment groups on gender, age and baseline Lobene stain scores. Analysis of covariance (ANCOVA), adjusted for baseline Lobene stain score as a covariate, was applied to compare inter-group differences in stain area, intensity, and composite scores at 4 and 8 weeks. Within each group, paired t-tests were used to

assess changes in Lobene stain scores between baseline and each follow-up time point (4 and 8 weeks). All tests were two-sided, with a significance threshold set at $\alpha=0.05$.

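### Does the three-arm trial lack its stated 80% power because the 20% difference has no reference mean and three groups are compared?

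*Combined protocol and SAP*

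**What the plan says.** The Sample size calculation section sets the spread in absolute units, "Assuming a standard deviation of 0.5 for Lobene stain area scores", and the target in relative units: to "detect a 20% difference between groups with 80% statistical power at a significance level of" 0.05, with 10% attrition. From these, "a sample size of 40 participants per group was determined to be necessary at baseline". The inputs are attributed to an earlier study of a whitening product. No reference mean, absolute difference, visit or test is given.

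Under Study population, the only stain threshold for entry is "a whole-mouth mean Lobene stain composite score greater than 1". Under Clinical assessments, area and intensity are each scored 0 to 3, and the composite is their product.

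The Statistical analysis section states the aim broadly: "Statistical analyses were performed to assess differences among the three groups". It plans a baseline-adjusted ANCOVA of area, intensity and composite scores at 4 and 8 weeks, all two-sided at 0.05. It lists no pairwise contrasts and no alpha split.

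**The concern.** A percentage cannot be set against a standard deviation in points without a base, so 40 per group cannot be rebuilt from the printed inputs. The number fits a simple two-group calculation, yet three groups are compared. If the base were low, or if alpha were shared over several contrasts, true power for a 20% difference would be well under 80%. A non-significant result against the manual brush could then be read as stronger evidence against a 20% effect than the design can give.

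**Working it through.** **Inputs.** From Sample size calculation: 40 per group, SD 0.5, 20%, 80% power, alpha 0.05, attrition 10%. From Statistical analysis: two-sided tests and baseline-adjusted ANCOVA. The reference mean is in neither section and is treated below as an assumption.

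**1. Reproducing the 40.** Evaluable per group: 40 × 0.9 = 36. Detectable difference, normal approximation:

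(1.960 + 0.842) × 0.5 × √(2/36) = 0.330 points.

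The exact two-sample t calculation gives 0.335. Dividing by 0.20 gives a reference mean of 1.65 (normal) or 1.67 (t). Forward from 1.67: difference 0.334; n = 2 × (2.802 × 0.5 / 0.334)² = 35.2, rounded up to 36; 36 / 0.9 = 40. The plan's number is recovered exactly under that mean.

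**2. Varying the unknown mean** (one pair, two-sided 0.05, no baseline adjustment):

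| Assumed reference mean | 20% of it | Enrolled n per group for 80% (normal) | Power with 36 (t) |
|---|---|---|---|
| 1.0 | 0.20 | 110 | 39% |
| 1.25 | 0.25 | 70 | 55% |
| 1.5 | 0.30 | 49 | 71% |
| 1.67 | 0.334 | 40 | 80% |
| 2.0 | 0.40 | 28 | 92% |
| 2.5 | 0.50 | 18 | 99% |

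The condition is therefore a floor of about 1.67, not a single value.

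**3. Does the entry rule settle the mean?** Composite is at most 3 × area, so a mean composite above 1 guarantees only a mean area above 1/3. That limit is approached only if every stained region has the darkest score. If every stained region scores intensity 1, the same rule forces a mean area above 1. It is a floor for individuals at baseline and says little about a group mean at 4 or 8 weeks, in either direction.

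**4. Three arms.** For the three-group F-test with 36 per group and a largest difference of 0.335, the noncentrality is 36 × Σ(mean − grand mean)² / 0.25:

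- Both sonic brushes equally far from manual: Σ = (2/3) × 0.335² = 0.0748; noncentrality 10.8; power 83%. This pattern reaches 80% at a reference mean of 1.61.
- One sonic brush midway: Σ = 0.5 × 0.335² = 0.0561; noncentrality 8.1; power 71%.

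Pairwise power at the same difference falls to 71% with alpha 0.025 and 65% with alpha 0.0167. Those levels would apply only if alpha were divided over two or three contrasts, which the plan does not do. At 0.05 each pair keeps 80%.

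**5. Baseline adjustment.** If 0.5 is an unadjusted SD, the ANCOVA residual SD is 0.5 × √(1 − r²), with r the baseline to follow-up correlation (not given; assumed). At r = 0.5 the residual SD is 0.433, the detectable difference is 0.335 × 0.866 = 0.290, and the reference mean needed drops to 0.290 / 0.20 = 1.45. To reach 80% at mean 1.2 (difference 0.24), r must be √(1 − (0.24/0.335)²) = 0.70; at mean 1.0 it must be √(1 − (0.20/0.335)²) = 0.80. At mean 1.67, r of about 0.42 would give 80% even at alpha 0.025, and about 0.50 at 0.0167. If 0.5 is already a change or residual SD, there is no such gain.

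**The case for a change.** The strongest case for acting is that one unstated input moves power from 39% to 92%, which is too wide to dismiss as wording. Eligible participants can have low area scores: area 1 with intensity 2 in every region gives a composite of 2 and a mean area of only 1.0. Even without any alpha split, power depends on an unstated pattern of means (71% or 83% for the F-test). If success meant that both sonic brushes beat the manual one, each at 0.05, power would be 69% at the implied difference. The correlations needed to rescue a mean of 1.0 or 1.2 are high.

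All of that arithmetic stands, and so does the observation that the 40 cannot be verified from the text. It does not show that the 80% is false. The mean may lie on either side of 1.67, and its likely source, the earlier study, is cited but cannot be seen here. The plan does not say that both brushes must succeed. Nor does it say that a null result will be read as excluding a 20% effect. The lack of multiplicity control is a question of false-positive error, and does not make the power statement wrong.

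The rewrite that would follow is also a poor one. It would replace the sponsor's design target with a difference worked back from n, by an unadjusted test where the plan uses ANCOVA, and add figures for alpha splits the plan does not contain.

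**Conclusion.** No change to the plan is called for. The sample size statement omits the base of the 20%, the comparison and visit it refers to, and whether 0.5 is an unadjusted, change or residual SD. None of its stated figures is shown to be wrong. Forty per group is coherent with 80% power for about 0.335 area points in one two-sided 0.05 comparison, and hence for a 20% difference whenever the reference mean area score is at least about 1.67. Below that mean power is lower, to 39% at 1.0, unless baseline adjustment makes up the loss. Above it power is higher.

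This rests on 36 evaluable per group, SD 0.5, and a reference mean and baseline correlation that the documents do not give. Writing down the missing items would leave enrolment, the ANCOVA and every result as they are. A reader of the results should in any case judge a null finding by its confidence interval, not by the planned power.

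### Do the gaps in how allocation concealment and examiner blinding are described call for a change to the plan?

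*Combined protocol and SAP*

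**What the plan says.** **Randomization.** Eligible patients received computer-generated numbers in ascending order "as they were enrolled in the study by an external dentist", and were then allocated to one of three groups. On access, the section says: "The external dentist responsible for randomization maintained exclusive access to the group allocation information throughout the trial". It adds: "All other study personnel remained blinded to the randomization information during the study".

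**Intervention.** "The distribution of the study products occurred at a separate location". On the people involved: "One study member was responsible for distributing the study products, while all other study members remained unaware of group assignments".

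**Clinical assessments.** Examinations at baseline, 4 weeks and 8 weeks were done "by a single investigator who was unaware of the type of toothbrush used by each patient". Their scope is also given: "The examinations included assessments of tooth stain as well as evaluations of both soft and hard oral tissues". At each follow-up, "an investigator asked patients about any adverse events during product use, including brushing discomfort". The section ends by saying that a facilitator stored the data after each session and that other personnel could not see participant data during the study.

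**Study Design.** The trial is labelled investigator-blinded. Patients are not described as blinded.

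**The concern.** Three things look wrong at first.

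1. **Concealment.** One reading of the Randomization section has the external dentist both enrolling patients and holding the list. Someone in that position could let the next assignment influence who enters and when. No envelopes, numbered containers or central release are mentioned, and nothing says that the baseline score is fixed before an assignment is released.
2. **Who knows.** One section gives sole access to the external dentist. The next has a study member handing out visibly different brushes, and that person must at least know whether each patient received a manual or a powered one.
3. **Examiner blinding.** Patients can see what kind of brush they have. They are asked about product use at follow-up, perhaps by the person who grades the stain. A remark at week 4 could colour the week-8 grading.

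The stake is the validity of the comparison. All efficacy outcomes are visual grades by one examiner, and no second rater is described. The planned ANCOVA adjusts for the baseline score. It cannot correct biased follow-up grading, or selection on anything the baseline score does not capture.

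**Working it through.** The plan gives no figure on this point to reproduce, so the check is mainly to set the statements side by side.

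**Step 1: order of events at entry.** Inclusion criterion 6 requires a mean composite score above 1, so stain must be scored before a patient can be eligible. Only eligible patients are numbered, and allocation comes after numbering. The order is therefore score, eligibility, number, group. The baseline examiner is stated to be unaware of brush type, and access to data is restricted after each session. This is not an explicit lock before release, but the described order already puts the score before the assignment.

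**Step 2: who could foresee an assignment.** The phrase naming the external dentist can attach to two verbs.
- If the dentist *assigned the numbers*, whoever enrolled is among the blinded personnel, and allocation by a third party is described.
- If the dentist *enrolled*, the list-holder is also the enroller, and concealment from that person is not shown.

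It would therefore be too strong to say that no concealment step is described. Sole access by an external person is one such step. What is unstated is the release mechanism and, on the second reading, the separation of roles.

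**Step 3: do the two statements on knowledge conflict?** They agree if the distributor is the external dentist. They also agree if the allocation information means the list itself and the external dentist is not counted as a study member. The text does not choose between these. They fail to agree only if the distributor is a second person and the blinding of all other personnel is read to cover brush type as well as the list. This is an ambiguity, not a demonstrated contradiction.

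**Step 4: the route to the examiner.** Blinding of the examiner is stated outright, and dispensing is at another site. The adverse-event questions cover discomfort, allergy and tissue changes; they do not ask about brush type. The text has a single investigator scoring stain and *an* investigator asking the questions. It neither equates nor separates them.

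**Step 5: scale of one grading step.** Inputs are from the Clinical assessments and Sample size calculation sections.
- Surfaces: 6 maxillary buccal + 6 mandibular buccal + 6 mandibular lingual = 18.
- Regions: 18 × 2 = 36. Criterion 5 requires 12 scorable anterior teeth, so all 36 apply.
- One area step in one region changes the mean area score by 1/36 = 0.028.
- The composite is area × intensity, so the same step changes the mean composite by 1/36 = 0.028 at intensity 1 and by 3/36 = 0.083 at intensity 3.
- Against the assumed area SD of 0.5: 0.028/0.5 = 0.056, about 6% of one SD, for one patient.

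This shows only how fine the scale is. It does not measure bias between groups and has no bearing on steps 1 to 3.

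**The case for a change.** The strongest case for acting is that subjective grading by one examiner makes blinding the main protection in this trial, and the plan asserts blinding more than it describes it. Separate dispensing does not stop a patient from mentioning the brush in the chair. On a natural reading of the Randomization section the enroller holds the list. The remedies look cheap: a lock-and-release step, one instruction to patients, and a different blinded team member for the adverse-event questions.

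Part of this stands. The release mechanism, the enroller, the distributor's identity, the adverse-event questioner and any instruction against disclosure are all unstated or ambiguous. If the distributor was a second person, the claim that everyone but the dentist was blinded needs qualifying.

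The rest does not carry. Silence about a procedure is not evidence that it was absent, and the document affirms the outcome each procedure is meant to secure. Unblinded patients are inherent in comparing manual with powered brushes and fit the investigator-blinded label. A second person for the adverse-event questions may mean extra staff, since the document does not describe who is available. The past tense and the March to July 2022 dates suggest that the trial is complete, in which case procedural remedies are no longer open and only wording remains.

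**Conclusion.** No change to the plan is needed. The concern identifies missing operational detail about properties that the plan does state: list access confined to an external dentist, allocation only after eligibility has been established by scoring, dispensing at a separate location, an unaware examiner and restricted data access. If those statements are true, the comparison is sound and nothing in the ANCOVA or the other analyses would be done differently.

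The size of any bias cannot be estimated from the document, and none is shown to exist; the 0.028 to 0.083 in the working is the scale of one grading step only. The conclusion assumes that the stated blinding held and that the enroller could not act on the next assignment. The text supports the first directly and the second on one of its two readings. Who enrolled, who dispensed and who asked the adverse-event questions are facts that the trial report can give in a few sentences, with its concealment and blinding claims limited to match.

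### The week-8 ANCOVA ignores week-4 scores from participants who leave later; one repeated-measures model per score would use them, at little cost and for a modest gain

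*Combined protocol and SAP*

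**What the plan says.** Under Clinical assessments, "Clinical examinations were conducted at baseline, 4 weeks, and 8 weeks by a single investigator". Under Statistical analysis, ANCOVA with the baseline score as its only stated covariate "was applied to compare inter-group differences in stain area, intensity, and composite scores at 4 and 8 weeks", and paired t-tests compare each follow-up visit with baseline within each group. The Sample size calculation sets 40 participants per group, "while also accounting for a 10% attrition rate". Nowhere do the documents mention a repeated-measures term, imputation or carry-forward, a rule for missed visits, or an analysis set. Study population makes "ability to attend all scheduled visits over the 8-week study period" a condition of entry.

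**The concern.** The plan expects to lose about 4 of 40 participants per arm (10%). Some of them will have been examined at week 4. Their scores enter the week-4 ANCOVA and the week-4 paired t-test. On the natural reading they do not enter the week-8 comparison, which uses only those examined at week 8.

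Week 8 is the final comparison of sonic with manual brushing. If participants with worse week-4 stain leave more often in one arm, the completers in that arm look better than the arm as randomised, and adjusting for baseline does not remove the difference. Equal overall dropout is no safeguard if the reasons for leaving differ by arm. The week-4 scores that would correct this part of the problem are already held.

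**Working it through.** **Inputs from the documents.** Sample size calculation: 40 per group at baseline, SD 0.5 (stated for the area score), 80% power, alpha 0.05, 10% attrition. Statistical analysis: two-sided tests. Clinical assessments: visits at baseline, 4 and 8 weeks.

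**Assumed, because the documents do not give them.** Dropout patterns by arm, the timing of dropout, the correlations between visits, and the absolute size of the effect.

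**Step 1: the plan's own figure.** 40 × (1 − 0.10) = 36 completers per arm. The detectable difference by normal approximation is 0.5 × (1.960 + 0.842) × √(2/36) = 0.330, or 0.335 with the t distribution. A difference of 0.330 is 20% of a mean of 1.65. The plan states the 20% but not the reference mean. Means of 1.0, 1.5 and 2.0 would need 99, 44 and 25 completers, hence 110, 49 and 28 enrolled. The figure of 40 can therefore be neither confirmed nor refuted. I take 0.335 as the working effect.

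**Step 2: precision under random dropout.** Let m be the completers per arm, n4 the number per arm with a week-4 score, and r the correlation of week-4 and week-8 scores given baseline and arm. Then

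variance(joint model) / variance(completer ANCOVA) = (1 − r²) + r² × m/n4.

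If all four dropouts leave after week 4 (m = 36, n4 = 40) and r = 0.7, this is 0.51 + 0.49 × 0.9 = 0.951. The standard error falls by 1 − √0.951 = 2.5%, effective size rises from 36 to 36/0.951 = 37.9 per arm, and power rises from 80.0% to 81.9%. For r from 0.3 to 0.9, the standard error falls by 0.5% to 4.1% and power is 80.4% to 83.2%. If half the dropouts leave before week 4, power is 80.2% to 81.7%. With no dropout at all it would be 84.0%.

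**Step 3: bias.** Simulation with 20,000 replicates per setting, 40 per arm, SD 0.5, true difference 0.335 and all dropout after week 4. The probability of dropout is logistic in the within-arm standardised week-4 score; OR is the odds ratio per SD. Correlations (baseline–week 4, baseline–week 8, week 4–week 8) are set A (0.7, 0.6, 0.85) and set B (0.5, 0.4, 0.7).

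The joint estimate uses two regressions: week 4 on arm and baseline in everyone, and week 8 on arm, baseline and week 4 in completers. The week-8 contrast is the arm coefficient in the second plus its week-4 coefficient times the week-4 arm effect. This is equivalent in likelihood to the repeated-measures model.

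| Dropout in the two arms | Completer-ANCOVA bias, A / B | Share of 0.335 |
|---|---|---|
| 10%/10%, OR 2 in both | 0.000 / 0.001 | about 0 |
| 10%/10%, OR 2 in one arm, random in the other | 0.0130 / 0.0165 | 4–5% |
| 12%/8%, OR 2 | 0.0055 / 0.0061 | 2% |
| 15%/5%, OR 2 | 0.0136 / 0.0162 | 4–5% |
| 20%/5%, OR 1.5 | 0.0122 / 0.0148 | 4% |
| 20%/5%, OR 2 | 0.0216 / 0.0242 | 6–7% |
| 20%/5%, almost exactly the worst week-4 scorers leave | 0.0578 / 0.0617 | 17–18% |

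Joint-model bias is at most about 0.001 throughout; Monte Carlo error is 0.0007 to 0.0008. With 10% random dropout per arm, the standard error falls from 0.0941 to 0.0913 (A) and from 0.1098 to 0.1073 (B), ratios 0.970 and 0.977. With 10% per arm at OR 2 the ratios are 0.977 and 0.986.

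**Step 4: a separate check with stronger selection.** Three arms of 40 with four dropouts in each, 4,000 runs. In the control arm, those with worse week-4 scores (plus random noise) leave; in the other arms dropout is random. Against a true −0.33, completer ANCOVA averages −0.295, −0.280 and −0.275 for r = 0.5, 0.7 and 0.9, a shortfall of 0.035 to 0.055 (11% to 17%) despite equal dropout rates. The joint estimate averages −0.329, −0.327 and −0.335.

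**Step 5: where the joint model falls short.** If dropout depends on the unseen week-8 score (20%/5%, OR 2), ANCOVA bias is 0.0297 / 0.0410 and joint-model bias 0.0126 / 0.0256. Then 0.0126/0.0297 = 42% to 0.0256/0.0410 = 62% of the bias remains.

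**The case against.** Baseline-adjusted ANCOVA at each visit is a standard, valid method, and these numbers largely show that it works. Even at 20%/5% with OR 2, the bias of 0.022 to 0.024 is under a quarter of a standard error of roughly 0.09 to 0.11. In a smaller simulation under the same assumptions, 95% intervals from the ANCOVA covered 94% to 95% in every setting except the near-worst one, where coverage was 90% to 91%. Nothing in the documents suggests that dropout differs by arm or follows stain score. The 20%/5% settings average 12.5%, above the planned 10%. Follow-up is short and entry requires the ability to attend every visit. The SD of 0.5 is given for area only, so the figures do not carry over directly to intensity or composite scores. With complete data the two methods give essentially the same week-8 estimate.

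All of this stands, and it limits the point to a modest improvement.

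Two further arguments carry less weight. An unstated carry-forward rule would make use of week-4 scores, but the text contains no such rule, and leaving it unstated would itself be a gap. The protocol also describes the trial as already conducted, so a new main model would be post hoc. That affects how the result must be labelled, not whether the method is sound.

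**Conclusion.** The concern holds as a cheap and modest improvement. As written, the week-8 contrast discards week-4 scores already held for later dropouts. The loss is negligible when dropout has the same rate and mechanism in each arm. It is about 2% to 7% of a 0.335 effect under moderate differences between arms, and 11% to 18% only under strong selection. The precision gain is 2% to 3% in standard error with 10% random dropout, provided all dropouts leave after week 4, and smaller otherwise.

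These sizes rest on assumed correlations, dropout patterns and effect size, none of which the documents supply. The direction of any bias cannot be known from them. Nothing here threatens the trial's validity.

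**What to change.** For each of the area, intensity and composite scores, fit one repeated-measures linear model to weeks 4 and 8. Include arm, visit, arm × visit, baseline and baseline × visit, with unstructured covariance and Kenward–Roger degrees of freedom. Include every randomised participant with any follow-up score, analysed as randomised. Report the week-8 contrasts; the planned week-4 contrasts come from the same model.

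Keep the per-visit ANCOVA as a sensitivity analysis. Add one for dropout not at random: impute missing week-8 scores, shift them by a range of values by arm, and report the shift at which the conclusion changes. Report dropout by arm and visit.

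The cost is a few lines of SAP text and a little more analysis work, with no new data. If results have already been seen, label the model as post hoc. The model assumes missingness at random given baseline, arm and week-4 score. It only partly corrects dropout driven by unseen week-8 scores, and it does not help participants with no follow-up visit.

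### Do unlabelled within-arm paired t-tests, run at the same 0.05 level as the ANCOVA, undermine the brush comparison?

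*Combined protocol and SAP*

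**What the plan says.** The Statistical analysis section opens with its purpose: "Statistical analyses were performed to assess differences among the three groups". The main tool is "Analysis of covariance (ANCOVA), adjusted for baseline Lobene stain score as a covariate", which "was applied to compare inter-group differences in stain area, intensity, and composite scores at 4 and 8 weeks". The section then turns to change within arms: "Within each group, paired t-tests were used to" "assess changes in Lobene stain scores between baseline and each follow-up time point (4 and 8 weeks"). One sentence sets the level for everything: "All tests were two-sided, with a significance threshold set at" 0.05. No test is called primary, supportive or descriptive.

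Two other places bear on the point. Study Design says that the trial "compared three toothbrush interventions". Sample size calculation sets the trial's size on a 20% difference between groups: "Assuming a standard deviation of 0.5 for Lobene stain area scores, a sample size of 40 participants per group". Under Intervention, all three arms receive a study brush, the same toothpaste and the same twice-daily, one-minute instruction; the control arm uses a manual brush.

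**The concern.** A fall from baseline within one arm mixes the brush with everything the arms have in common: the toothpaste, the brushing instruction and being in a trial. A paired t-test cannot separate these. If the paired tests stand level with the ANCOVA, a report could set a significant fall in a sonic arm beside a non-significant fall in the manual arm and present the pair as evidence for the sonic brush. That inference is invalid, because the difference between the two changes has not been tested. The trial's title is about how well two sonic brushes reduce stain, and a significant within-arm fall could seem to answer that. The paired tests also outnumber the ANCOVA comparisons three to one, and no rule says which set carries the efficacy conclusion.

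**Working it through.** **Inputs from the documents.** Three arms; three scores (area, intensity, composite); two follow-up visits; 40 per group with 10% attrition; area SD 0.5; two-sided 0.05.

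**Assumptions.** Identical brushes, a common fall from baseline in all arms, and a baseline to follow-up correlation r. The documents give no expected fall and no r, so ranges are shown.

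**1. What the sample size is for.** Completers per arm: 40 x 0.9 = 36. Difference detectable between two arms with 80% power: 0.5 x sqrt(2/36) x (1.960 + 0.842) = 0.330. If that is 20% of a mean, the mean is 0.330 / 0.20 = 1.65. The plan states no reference mean, so the figure of 40 cannot be fully reproduced. It is nevertheless a between-group calculation, and the paired tests play no part in it.

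**2. Count of tests.** Paired: 3 x 3 x 2 = 18, taking the stain scores to be the three named in the ANCOVA sentence just before. If only one score were meant: 3 x 1 x 2 = 6. ANCOVA comparisons: 3 x 2 = 6.

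**3. What each analysis estimates.** The mean change in an arm is the brush effect plus the shared effects. Subtracting one randomised arm from another removes the shared part, and the baseline-adjusted ANCOVA makes that comparison. This holds whether or not an untreated arm exists: a within-arm test could not isolate a brush effect even if one were added.

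**4. How often the paired tests alone would mislead.** Let p be the chance that one arm shows a significant fall (noncentral t, n = 36). The misleading pattern is at least one sonic arm significant and the manual arm not: (1 - (1 - p)^2) x (1 - p). Example at a fall of 0.3 SD of change: p = 0.417, so (1 - 0.583^2) x 0.583 = 0.660 x 0.583 = 0.385.

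| Shared fall (SD of change) | Each arm significant | Misleading pattern |
|---|---|---|
| 0.1 | 8% | 15% |
| 0.2 | 21% | 30% |
| 0.3 | 42% | 38% |
| 0.4 | 65% | 31% |
| 0.5 | 83% | 16% |
| 0.6 | 94% | 6% |

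Outside this grid the pattern is rare: 1.7% at 0.7 SD and, with no fall at all (p = 0.025), (1 - 0.975^2) x 0.975 = 4.8%.

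**5. In area points.** SD of change = 0.5 x sqrt(2(1 - r)), which is 0.500 at r = 0.5 and 0.224 at r = 0.9. The peak at 0.3 SD is then a shared fall of 0.15 down to 0.07 points. For r of at least 0.5, a fall of 0.3 points or more gives the pattern in 6% of trials or fewer. At r = 0.3 the SD of change is 0.592 and p = 0.841, so the figure is (1 - 0.159^2) x 0.159 = 15.5%.

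**6. What the planned ANCOVA does in the same trials.** Simulation of three identical arms of 36, r = 0.5, 0.8 and 0.95, 40,000 trials per setting: the ANCOVA rejects in 4.8% to 5.1%. The misleading pattern occurs together with a significant ANCOVA in 0.9% to 2.8%, and with a non-significant ANCOVA in 4.9% to 35.9%. Among trials with the pattern, the ANCOVA is non-significant in about 83% to 93%.

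**7. Multiplicity.** If the tests were independent, the chance of at least one false rejection would be 1 - 0.95^18 = 0.603 for the paired tests and 1 - 0.95^6 = 0.265 for the ANCOVAs. The 0.603 concerns the hypothesis that no arm changes at all, which is not the trial's question. Labelling the paired tests leaves the 0.265 where it is.

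**The case for a change.** The best case for a change is that it would cost one sentence. The plan never ranks the tests. The between-group aim has to be inferred from the opening line and the sample size, and step 6 shows that paired tests and ANCOVA can point different ways in up to about 36% of trials with no true brush difference. Saying beforehand which result counts would close off a common misreading.

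Part of this stands. No rank is stated, the arithmetic is right, and a sentence in the report calling within-arm changes descriptive would be good practice.

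The rest does not carry. Change within an arm and difference between arms are different quantities, so a mixed pattern is not a contradiction that needs a tie-break rule. The plan uses the paired tests to describe change over time, a legitimate question, and nowhere credits that change to a brush. The percentages apply only if a reader discards the planned comparison, and their size depends on a shared fall that the documents do not give.

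The further remedies that might be attached add little. A 95% confidence interval for mean change carries the same information as the paired test. Contrasts of each sonic brush with manual would spell out the between-group comparison already planned, but would need their own multiplicity rule, which is a separate matter. Regression to the mean after entry at a composite score above 1, if the entry score is also the baseline, could add to the within-arm falls, but it does not bias the between-arm ANCOVA.

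**Conclusion.** The concern does not call for a change. The observation is accurate: the paired tests share the 0.05 threshold with the ANCOVA and carry no descriptive label. But the analysis that can answer the trial's question is already planned for every score at both visits, adjusted for baseline, with a simulated error rate of about 5% per test. The stated aim and the sample size point to the same comparison. Following the plan as written gives sound between-arm conclusions, and a label would alter no between-arm estimate, sample size or error rate. The 6% to 38% is how often someone reading only the paired tests would see a brush difference that is not there. It is not a false-efficacy rate for this plan. It rests on 36 completers per arm and an assumed shared fall of 0.1 to 0.6 SD of change, and it drops to 1.7% at 0.7 SD. The gap is one that analysts fill sensibly by reporting the within-arm changes as description.
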